10 SUBJECT PAYMENT

11 STUDY MANAGEMENT AND ADMINISTRATIVE PROCEDURES

11.1 Training and Monitoring

The investigators and site research staff will be trained on the study procedures. Sponsor representative(s) may be present at the site during the treatments to ensure that all procedures and documentation are in place.

Investigator will allow sponsor representatives to periodically review the study documentation. Monitoring of the site will occur at regular intervals to evaluate the progress of the study, verify the accuracy and completeness of CRFs against subject source documentation, assure that all protocol requirements, applicable FDA regulations and the investigator's obligations are being fulfilled and resolve any inconsistencies in the study records.

11.2 Informed Consent

The investigator is responsible for ensuring that written informed consent, using an Institutional Review Board (IRB) approved informed consent document, is obtained from each subject before the performance of any protocol procedures, including administration of the study device. The informed consent document must comply with all essential elements as defined in 21 CFR 50.25 "Elements of Informed Consent" and must contain a statement that consent is freely given, the study involves research, the subject is aware of the risks and benefits of entering the study, and that the subject is free to withdraw from the study at any time. An evaluation of each candidate will be conducted by the investigator. Upon determining a subject's eligibility status, the subject will be offered the opportunity to participate in the study.

The investigator or the investigator's designee will inform all subjects regarding the purpose of the study and expected duration, as well as the potential risks and benefits that may result from participation. The subjects shall be informed by the investigator or investigator's designee that they are free to refuse participation in this clinical study. If they elect to participate, it will be made clear that they may withdraw from the study at any time without prejudicing further care.

The subjects will also be informed of alternative methods of treatment should they not wish to participate in the study.

The subjects will be given the opportunity to discuss the procedure, risks, benefits, alternative therapies, and the study requirements with the investigator and have any and all questions answered to the subjects' satisfaction. A signed and dated informed consent form must be obtained from the subject by the Investigator or the Investigator's designee prior to a subject's involvement in the study.

The acquisition of informed consent will be documented in the subject's medical records, as required by 21 CFR 812.140. A copy of the consent form will be given to the subject. The original consent forms will be kept in the CRF binder by the investigator and will be subject to review by Cutera or a representative of Cutera, and by appropriate regulatory bodies.

11.3 Protocol Compliance

The principal investigator must comply with all terms of the protocol.

11.3.1 Protocol Amendments

Neither the principal investigator nor the sponsor will modify or alter this protocol without first obtaining the concurrence of the other party (with the exception of amendments which involves mitigating a medical emergency or immediate health risk to the subject). The party initiating an amendment must confirm it clearly in writing and it must be signed and dated by the sponsor and the principal investigator. IRB approval must be obtained before implementation of an amendment.

11.3.2 Protocol Deviations

All protocol deviations must be clearly described on the case report form (i.e., Cutera Protocol Deviation Form). Deviations from the protocol may include but are not limited to subject's failure to attend scheduled visit during a visit window, use of out of range treatment parameters and incomplete or

incorrect study procedures. Any medical emergency or immediate health risk to the subject which results in a protocol deviation and must be reported to the sponsor within 5 working days

Significant protocol deviations must be reported to IRB according to their policies.

11.4 Study Personnel

Prior to the start of the study, the investigator must supply the sponsor with a list of the names and curricula vitae that describe the professional backgrounds of the clinically responsible study investigators (principal, sub-investigators), research nurses, and other possible participants (e.g. medical doctor, nurse, etc.).

11.5 Disclosure of Financial Interest

Each investigator [principal and sub-investigator(s)] is required to disclose sufficient accurate financial information to the sponsor, to allow sponsor to submit complete and accurate certification or disclosure statements.

11.6 Data Collection, Record Keeping and Storage

The principal investigator is responsible for assuring that all study records including case report forms (CRFs), informed consent forms, device accountability records, source documents (e.g., medical records, histology reports etc.) and other study records are complete, accurate and recorded in a timely manner.

CRFs should not be the only record of a patient's participation in the study and will be used for transcribing data from source documents which are the point of first entry of data collected for each subject (with the exception of documents listed under **B**). The investigator or research staff at the site will ensure that:

A. Source documentation thoroughly and adequately documents:

1. That patient is participating in a clinical study and has been properly informed and consented prior to participation in the study,
2. Medical history,
3. Concomitant medications,
4. Patient's condition upon entering and during the course of the study,
5. Any adverse event(s) that might have occurred (in addition to the Visit CRFs and/or Adverse Device Effect CRF and/or Cutera SADE form completed),
6. Results of any diagnostic tests/histology conducted during the study.

B. The following data will be recorded directly onto CRFs:

7. Patient meets study inclusion and exclusion criteria,
8. A record of the treatment parameters, including the date of each RF treatment and any other adjunct therapy, a drawing of the patients abdomen showing the treatment location, and the vial numbers containing control and treatment biopsies,
9. Any protocol deviations,
10. Subject Questionnaire(s),
11. Study related improvement assessments by the investigator or investigator's designee,

12. Treatment-related pain ratings.

C. The following documents will be maintained in the study records:

13. The Investigator or the research staff will check signed informed consent for accuracy and will always keep the original copy of the signed informed consent in the CRF binder.
14. All correspondence with an Institutional Review Board (IRB), the sponsor, or FDA including required reports will also be retained in the study records.
15. Records of receipt, use or disposition of the investigational device.

All data entries on the CRFs will be recorded completely, promptly, and legibly using blue or black indelible ink pen and accuracy will be ensured. The corrections on CRFs will be made only by the investigator or the documented investigator's designee. To make a correction to an entry, the data will be crossed through with a single line (the original entry should be visible) and then will be initialed and dated by the person making the correction.

The study records will be maintained in a secure location throughout the duration of the study. Upon study completion or termination, records will be kept at a secure location until at least 2 years after the last approval of a marketing application and until there are no pending or contemplated marketing applications or at least 2 years have elapsed since the formal discontinuation of clinical development of the investigational product.

11.7 Subject Confidentiality

This study preserves the confidentiality of all subjects under the Health Insurance Portability and Accountability Act of 1996 (HIPAA) Privacy Rule. The following safeguards will be in place to protect the privacy of the individuals who are the subjects of the health information to be used in the research and the confidentiality of that information:

The subjects will be informed by the investigator or the investigator's designee that their medical records will be kept as confidential as possible but may be subject to review by: (1) Cutera, or its representative; (2) reviewing IRB; and/or (3) by appropriate regulatory bodies (e.g. the US Food and Drug Administration (FDA), Department of Health and Human Services (DHHS) agencies).

Only pieces of personal information required for purposes of the study will be collected. The personal information will be collected and used to ensure subject eligibility for study participation, to conduct the study and to assess the results of the study as required and permitted by law. Subjects have the right to see and copy any of the information gathered about them and request changes if the information is not correct, until it is no longer kept by the investigator. Permission to use or disclose personal information, except for that has been collected and relied on may be cancelled by the subject by written notice. If the subject is withdrawn from the study, the information collected to that time may still be used to preserve the scientific integrity of the study. There is no expiration date to this authorization.

Subjects' identities will be kept confidential. Subjects will be assigned a unique study code that will not reveal the subjects' identity, and this code will be used on all study documents. To protect subject identity with regards to the photographs taken of the treatment areas, care will be taken to cover areas of photographs to protect identity. Techniques such as covering of eyes on full face photographs,

cropping off portions of the face in close-up photos will be used to obscure identifying characteristics in photographs. The results of research, including photographs, may be published in scientific journals, presented at medical meetings, and used in training and marketing materials but subject identities will not be disclosed.

Appendix 1: Study Schedule

[figure not shown]

Appendix 2: Pain Rating Scale

Subjects will be instructed to rate the pain associated with RF treatment by indicating a number that best represents the overall average pain experienced using the following scale:

Appendix 3: Fitzpatrick Skin Type Classification

Appendix 4: Before and After Treatment Instructions

Before Treatment Instructions:

- The day before and the day of your truSculpt treatment, drink plenty of water to ensure you are well hydrated. The truSculpt treatment works best when patients have had plenty of fluids prior to treatment.

After Treatment Care Instructions:

- Redness is expected and should resolve within a few hours.
- Mild swelling may occur and should go away within 72 hours.
- Tenderness of the treatment area may persist up to 1 week.
- Avoid hot showers or baths and avoid scrubbing the treated area when bathing.
- Please call your study doctor if you experience any of the following in your treatment area:
 - Blistering
 - Bleeding
 - Burn
 - Crusting or scabbing
 - Pain or Tenderness, Redness or Swelling that lasts more than 72 hours
 - Nodules or lumps
- Do not pop or un-roof blisters if they occur.
- If you need to take any over-the-counter medications for discomfort after the RF treatment, take non-aspirin pain medications, such as Tylenol or Advil.

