4.2 Study Duration

Subjects enrolled in this trial will be asked to participate for up to 3 months and will complete 3 visits: 1 screening visit, 1 RF treatment visit, and 1 follow-up visit (biopsy collection visit) on the day of their planned abdominoplasty surgery.

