6.2 RF Treatment Visit

The following procedures will be performed at the RF Treatment Visit:

1. If needed, cleanse subject's treatment area with a mild cleanser to remove any cosmetics, perfume or lotions and then dry the area.
2. Prior to performing RF treatment, the Investigator should confirm the subject continues to meet the study eligibility criteria, including asking about any changes in medical history and/or concomitant medications or significant increase or decrease in subject weight.
3. Using a surgical marker, mark the subject's abdomen as it will be marked on the day of the subsequent planned abdominoplasty procedure.

4. Place the return pad on the subject's upper lateral back. Connect the neutral electrode cable after the return pad has been applied.
5. The subject should be lying down and comfortable while undergoing RF treatment and the operator should have easy access to the treatment area.
6. Conduct RF treatment according to the parameters listed in Table 2 with one imprint applied to the subject's abdomen over the tissue intended to be removed during the following abdominoplasty procedure.

Table 2. TruSculpt RF Device Treatment	
RF Power	[REDACTED]
Pulse Duration	[REDACTED]
Frequency	[REDACTED]
Target Skin Temperature	[REDACTED]
Handpiece Size	[REDACTED]

7. Place the handpiece on the skin of the area to be treated and ensure the electrode is in full contact with the skin at all times. Do not apply excess pressure as this may diminish treatment effects and cause additional subject discomfort. The operator must wear surgical gloves during RF treatment.
8. After the imprint is delivered, an image will be taken of the subject's markings and post-treatment hyperemia pattern showing the location of the imprint. The image will be added to the subject's chart. The pulse duration for the imprint and the target temperature achieved during RF treatment will be recorded in the subject's chart.
9. The subject will be asked to rate the average level of discomfort experienced during and after completion of treatment using the Pain Rating Scale found in Appendix 3.
10. Investigator will assess and record any immediate post-treatment adverse device effects.
11. The "Before and After Treatment Instructions" will be explained and provided to the subject (see Appendix 4).

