6.3 Biopsy Collection Visit

The Biopsy Collection visit will occur on the same day as the abdominoplasty surgery. The following procedures will be performed prior to and during abdominoplasty surgery:

1. Review of subject medical history.
2. Assess and record any additions, changes and/or deletions in prescription and nonprescription concomitant medications since the previous study visit.
3. Record severity and duration of any adverse device effects following RF treatment and assess for any new adverse device effects.
4. Biopsy collection procedure:
 - a. Refer to the patient chart and identify the RF treatment location.
 - b. During the biopsy collection procedure, at least one skin biopsy (approximately 10 mm x 10 mm; full thickness) will be taken from the area treated with RF; and at least one skin biopsy (approximately 10 mm x 10 mm; full thickness) will be taken from an equivalent contralateral non-treated area as a control.

c. Each biopsy sample will be immediately placed in the prepared fixative vials, making sure the samples are fully submerged in the solution. The vials will be labeled with the subject ID number, subject initials and biopsy date. The vials will be randomly numbered, and the numbers of the vials containing the biopsy from the RF treated and control skin will be recorded in the patient chart. The histologist will remain blinded to the nature of each biopsy sample (treatment or control).

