7.2 Recording Adverse Device Effects

All potential ADEs will be evaluated and must be recorded in the subject's medical chart and in the study case report forms. ADEs will be monitored and tracked from the time of the first RF treatment.

At each contact with the subject, the Investigator will seek information on ADEs by specific questioning and, as appropriate, by examination. ADEs may be observed by the Investigator and/or clinical research staff, elicited from the subject and/or family member or volunteered by the subject. All observed and volunteered adverse signs and symptoms (both expected and unexpected), regardless of severity or frequency, will be recorded in the case histories (medical chart and CRFs). Included in the description should be the nature of the sign or symptom, the date of onset, date of resolution (duration), the severity, whether the event was expected or unexpected (anticipated or unanticipated), the relationship to study treatment or other therapy, the action taken (if any), and the outcome.

All SADEs and UADEs must be reported according to Cutera and IRB requirements.

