8 POTENTIAL RISKS / BENEFITS

8.1 Potential Risks

The known risks and adverse device effects associated with the study device or treatment procedure are shown in Table 3.

Table 3. Potential Study Risks

Table 3. Potential Study Risks or ADEs/SADEs			
STUDY DEVICE/PROCEDURE RELATED			
Type of Adverse Device Effect	Severity	Expected Duration	Frequency
Abrasion	Mild to Severe	3-14 days	Very Rare
Bleeding	Mild	Up to 1 hour	Very Rare
Blanching	Mild	> 24 hours	Very Rare
Blistering	Mild to Severe	1-14 days	Rare
Burn	Moderate	1-3 weeks	Rare
Contour Abnormalities/Cutaneous Depressions	Mild to Severe	> 1 month	Uncommon

Crusting/Scabbing	Mild to Severe	3-14 days	Rare
Edema (Swelling)	Mild to Moderate	< 72 hours	Very Common
Erythema (Redness)	Mild to Moderate	< 24 hours	Very Common
Hyperpigmentation	Mild to Severe	> 1 month	Rare
Hypopigmentation	Mild to Severe	> 1 month	Very Rare
Infection	Mild to Severe	2-14 days	Rare
Palpable nodules	Mild to Moderate	> 1 month	Common
Oozing	Mild to Severe	2-14 days	Very Rare
Pain (Discomfort)	Mild to Severe	During procedure	Very Common
Purpura (Bruising)	Mild to Moderate	7-21 days	Common
Scarring	Mild to Severe	> 1 month	Rare
Textural Changes	Mild to Severe	> 1 month	Rare
Partial, over treatment, and/or no treatment with the study device(s) due to equipment problem (device malfunction)	Mild to Severe		Rare
Improper treatment (partial, over-treatment, and/or no treatment) with the study device(s) due to user error	Mild to Severe		Rare
Unintended injury to subject, user or others due to user error (e.g., unintentional treatment to non-target location)	Mild to Severe		Rare

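### Minor safety gap: the Appendix 4 call list names neither infection nor oozing, and makes pain, redness and swelling wait 72 hours even if they worsen

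*Combined protocol and SAP*

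**What the plan says.** Appendix 4 is the handout explained and given to the subject at the RF treatment visit (6.2, step 11). Its call list opens "Please call your study doctor if you experience any of the following in your treatment area" and has six entries: blistering; bleeding; burn; crusting or scabbing; "Pain or Tenderness, Redness or Swelling that lasts more than 72 hours"; and nodules or lumps. Only the fifth carries a waiting time. The same page says that redness should clear in a few hours, that swelling should be gone within 72 hours, and that tenderness can last as long as a week.

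Table 3 in 8.1 gives the two risks at issue as "Infection Mild to Severe 2-14 days Rare" and "Oozing Mild to Severe 2-14 days Very Rare".

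Section 4.2 sets out the visits as "1 screening visit, 1 RF treatment visit, and 1 follow-up visit (biopsy collection visit) on the day of their planned abdominoplasty surgery". Section 7.2 states: "At each contact with the subject, the Investigator will seek information on ADEs by specific questioning". On the day of surgery, 6.3 step 3 requires staff to "Record severity and duration of any adverse device effects following RF treatment and assess for any new adverse device effects". The RF imprint is applied "over the tissue intended to be removed during the following abdominoplasty procedure" (6.2, step 6).

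**The concern.** Between RF treatment and the day of surgery, the readable text describes no visit or telephone contact. During that time the investigator learns of an adverse effect only if the subject gets in touch, so the handout matters more than it would in a study with interim follow-up.

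A subject who follows the page literally is not prompted by oozing, drainage or fever as such. The subject is also told to act on pain, tenderness, redness or swelling only after 72 hours, even if the symptom is clearly getting worse.

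The protocol itself treats infection at this site as important. Infection in the target area is exclusion criterion 11 (5.1.2), and 5.3 allows a subject who develops an exclusion criterion to be discontinued. The treated tissue is also due for surgery. The stake is timely reporting of an uncommon safety event, and with it time to treat the infection or reschedule the operation.

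**Working it through.** The plan states no figure to reproduce. The check sets the call list beside Table 3 and the visit schedule, with some simple arithmetic.

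**1. Call list against Table 3.**

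| Table 3 risk | Table 3 frequency | On the call list? | Wait |
|---|---|---|---|
| Blistering | Rare | Yes | None |
| Burn | Rare | Yes | None |
| Crusting/scabbing | Rare | Yes | None |
| Bleeding | Very Rare | Yes | None |
| Infection | Rare | No | – |
| Oozing | Very Rare | No | – |

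Rarity does not explain the omission, because four other risks in the same frequency bands have an entry.

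**2. The 72-hour wait against the expected course.**
- Redness: Table 3 gives erythema under 24 hours. Redness still present between 24 and 72 hours is outside the expected course, yet no call is asked for. That gap is 72 − 24 = 48 hours.
- Swelling: Table 3 gives edema under 72 hours, so the wait fits.
- Tenderness: the page allows up to a week but asks for a call after 72 hours, which is a mixed message.

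**3. Size of the delay, counted from symptom onset.** Inputs: the wait (Appendix 4) and the expected duration of infection, 2–14 days (Table 3).
- Wait: 72 / 24 = 3 days.
- Infection lasting 14 days: 3 / 14 = 21% of its course has passed when a call falls due, with 14 − 3 = 11 days left.
- Infection lasting 2 days: 2 < 3, so the trigger is never met.

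These figures are illustrative. They assume that the visible signs last as long as the infection, which Table 3 does not say.

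**4. Size of the delay, counted from RF treatment.** Wait = max(0, 3 − onset day), where onset day is counted from treatment. It is 3 days for onset on day 0 and 0 days for onset on day 3 or later.

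**5. Signs that start shortly before surgery.** Let surgery be on day S and onset on day S − x, with x < 3.
- Counted from onset, the trigger falls on S − x + 3, which is later than S. The signs may then first be assessed on the day of surgery.
- Counted from treatment, the trigger falls at day 3 after RF. The gap disappears unless surgery follows within about 3 days of RF.

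The RF-to-surgery interval is not in the readable text. Section 4.2 gives only total participation of up to 3 months.

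**The case against.** The strongest reply is that nothing is shown to be missed. The check in 6.3 is among the procedures done before and during surgery, so an unresolved infection should be found before the operation, and its severity and duration recorded. This stands. A reader might infer that infected tissue would go unnoticed into surgery, that the safety table would be materially undercounted, or that the histology endpoint would suffer. The documents support none of these.

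A reader might also infer that, whatever the interval to surgery, signs starting in the last 72 hours cannot meet the trigger beforehand. That holds only if the clock starts at symptom onset. The list follows advice on normal recovery, including the 72-hour limit for swelling, so a subject could reasonably count from treatment. The claim has to be conditional on the onset reading.

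Three further points stand in part:
- Blistering, bleeding, burn, crusting and nodules prompt a call with no wait, so some infections, and oozing that comes with one of these signs, would be reported early.
- The list does not forbid calls about other symptoms, and 7.2 records whatever a subject volunteers. Even so, a page that states a waiting time can be expected to make some subjects wait.
- The Appendix 1 schedule, the consent text and part of section 4 cannot be seen and may contain an interim contact or another prompt. Such a prompt would reduce the consequence but would not correct the page the subject takes home.

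**Conclusion.** The point holds as a minor safety improvement. Two facts rest on the text alone: infection and oozing are listed risks missing from the call list, and the 72-hour line has no exception for worsening and does not match the expected course of redness.

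The consequence is possible late reporting of an infection shown only by pain, tenderness, redness or swelling. The delay is up to about 3 days if the clock starts at onset, and 0 to 3 days if it starts at treatment. The number of subjects affected is probably very small, given events rated Rare and Very Rare and about 14 subjects with one imprint each.

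The conclusion assumes that subjects follow the page as written and that no interim contact exists in the parts that cannot be seen. It has no bearing on the histology endpoint, and its effect on the adverse-effect tabulation is small.

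**What to change.** Add one bullet to the Appendix 4 call list, to be reported at once: *Oozing or drainage, fever, or other signs of infection, or redness, swelling, pain or tenderness that gets worse at any time.* Keep the 72-hour line for symptoms that persist without worsening. Optionally, add the words *even if mild* to that line, so that the advice about a week of tenderness does not discourage a call.

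The cost is a few more calls in the first 72 hours, since Table 3 rates edema and erythema Very Common and some subjects will call about an expected reaction. Because Appendix 4 is part of the protocol, 11.3.1 also requires a written amendment signed by the sponsor and the principal investigator, with IRB approval before use.
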